Appendix C: Flow Chart of Suggested Diagnostic Approach for Assessing Suspected Recurrent VTEs

Appendix D: Collection of Clinical Predictors for Suspected Recurrent VTE

Presenting history

Age
Gender
Duration of symptoms (days)
Inpatient/outpatient
Any dyspnea
Sudden dyspnea
Any chest pain
Pleuritic chest pain
Sudden chest pain
Hemoptysis
Affected leg: left/right
Leg pain
Cramps in the leg
Pruritus of the leg
Heaviness of the leg
Paraesthesia of the leg
Symptoms worse after walking and standing
Symptoms worse at end of the day
Symptoms best first thing in morning
Symptoms improve with rest or elevating leg
Symptoms worse after prolonged standing (>2 h, > 6 h)
Symptoms relieved after elevating leg
Symptoms relieved with compression stockings
Current use of anticoagulant therapy
Type and dose of anticoagulant therapy (e.g. LMWH, warfarin, NOACs)
Anxious personality

Risk factors

Family history of VTE (first and second degree)
Known thrombophilia
Pregnancy
Post-partum (<6 weeks after delivery)
Recent surgery (< 4 weeks, 8 weeks, 12 weeks)
Orthopedic surgery (< 4 weeks, 8 weeks, 12 weeks)
Active malignancy (< 6 months; malignancy required therapy, recurrent or metastatic, palliative)
Recent immobilization (< 10% walking hours for 3 consecutive days < 4 weeks, 8 weeks, 12 weeks)
Major trauma (< 4 weeks, 8 weeks, 12 weeks)
Congestive heart failure

Estrogen use
Paralysis of the leg
Paresis of the leg
Recent plaster cast (< 4 weeks, 8 weeks, 12 weeks)
Long distance flight (< 4 h, < 8 hours, < 12 hours, 12 hours and more), within 4 weeks, 8 weeks and 12 weeks

Characteristics of previous event and period between current and previous event

Number of previous events
Previous event: DVT/PE
Provoked/unprovoked
Time between previous event and current suspected recurrence
Location of previous event (in case of PE: central, lobar, segmental, subsegmental)
Location of previous event (in case of DVT: proximal, distal)
In case of DVT, affected leg (left/right)
Duration of anticoagulation
Type of anticoagulation (e.g. UFH, LMWH, warfarin, NOACs)
Previous use of compression stockings
Current use of compression stockings
Duration of use of compression stockings
Residual thrombosis present on baseline imaging
D-dimer test result after stopping anticoagulation

Physical examination

Height
Weight
O₂ Saturation
Heart rate
Respiratory rate
Temperature
Systolic blood pressure
Diastolic blood pressure
Crackles
Swelling of the whole leg
Redness of the leg
Warmth of the leg
Calf pain
Calf diameter of symptomatic leg
Calf diameter of asymptomatic leg
Superficial vein dilatation of the leg
Localized tenderness along the deep venous system
Pitting edema
Telangiectasia
Erythema
Varicose veins

Pigmentation
Eczema
Lipodermatosclerosis
Pretibial edema

ECG changes

ST changes
T wave changes

Chest x-ray

Parenchymal change
Band atelectasis
Elevation of hemidiaphragm

Laboratory test

D-dimer test
INR
INR values over the last 4 weeks
CRP (C-reactive protein)
pro – BNP (Brain natriuretic peptide)

Physician impression

Likelihood of recurrent DVT(%)
Likelihood of recurrent PE (%)
Another diagnosis more likely

Patient impression

Patient recognizes the symptoms from previous event(s)

Appendix E: Adjudication of Suspected Recurrent VTE Events

Recurrent VTE

Recurrent VTE will be excluded if participants have a low/intermediate or unlikely pre-test clinical probability with the Geneva or Wells rule and a negative D-dimer test result.

Recurrent Deep Vein Thrombosis

Recurrent DVT will be ruled out if participants have a normal ultrasound (fully compressible veins) or an unchanged/improved incompressible segment as compared with baseline when available.

The criteria for diagnosis of recurrent DVT will be:

1. Compression ultrasound revealing a new (compared to baseline/index ultrasound) area of non compressibility of a venous segment above the trifurcation of the popliteal vein will be considered diagnostic of a deep vein thrombosis.
-OR-
2. Venography demonstrating a constant intraluminal filling defect in the deep veins above the trifurcation of the popliteal vein will be considered diagnostic of a deep vein thrombosis.

Recurrent Pulmonary Embolism

1. If the V/Q scan is normal or unchanged from baseline/index imaging, PE will be considered excluded.
2. If the V/Q scan is non-normal and a new unmatched segmental or greater perfusion defect is documented then recurrent PE will be diagnosed.
3. If a new matched or subsegmental perfusion defect is documented the test won't be considered positive for PE.
4. If participants receive a spiral CT scan and an intraluminal filling defect is seen in a segmental or greater vessel that was previously free of thrombus, pulmonary embolism is diagnosed. If the CT scan is normal or unchanged as compared with baseline, PE will be considered excluded.
5. Pulmonary angiography demonstrating a constant intraluminal filling defect or a cutoff of a vessel > 2.5 mm in diameter will be considered diagnostic for PE.

Death

All deaths during follow-up will be adjudicated as to the likelihood that the death was related to PE. The following criteria will be used: *Certain*: hypotension, hypoxia, cardiac arrest with no other explanation than PE, autopsy or radiographic confirmation; *Highly probable*: criteria for certain but another disease could have caused the death; *Probable*: other cause suspected based on clinical evidence but 100% certainty not available; *Unlikely*: all other cases.

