6.2.2 D-dimer testing

All study patients will have a blood sample drawn at the time of suspected recurrence and frozen for central D-dimer testing. Serum samples will also be stored for future potential predictor assessment (other D-dimer assays or other biomarkers). Samples will be shipped in batches to the coordinating site and D-dimer levels will be determined in all patients using a single commercial assay (VIDAS D-dimer Exclusion II, bioMérieux Inc, Durham, NC). Please refer to the resource manual for details on processing, storage and shipping of D-dimer samples.

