6.3 Follow-up Visits

All patients in whom a recurrent VTE is ruled out will receive a follow-up call at 3 months (90 ± 7 days) after the initial evaluation using a structured interview script. Research coordinators will be trained by the investigator or multicenter coordinator prior to follow-up to ensure consistency in eliciting new signs and symptoms of DVT and PE between sites. Any new leg or chest symptoms reported to study personnel during study follow-up will prompt clinical and diagnostic assessment. Participants with suspected VTE will be assessed in the Thrombosis Clinic (or Emergency Department) and ordered diagnostic testing as judged necessary by their physician or the investigator. If participants report that they sought medical attention for complaints of possible VTE, medical records and imaging results will be collected to prepare an adjudication report. Any participant who seeks medical attention during their follow-up period and is once again not diagnosed with a recurrent VTE will have an additional call at 90 (± 7 days) days after they were last assessed.

All deaths during follow-up will prompt chart review and all available information including interviews with next of kin will be documented to permit preparation of an adjudication report to determine if the death is PE related.

The follow-up period is relatively short and therefore participant loss to follow-up should be minimal. However, for participants that cannot be reached by phone, an exhaustive search will determine if outcome events have occurred (including calls to next of kin or pre-identified contacts, obituary searches, retrieval of death certificates, review local hospital databases) prior to participants being declared lost to follow-up.

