9.5 Primary Outcome Analysis

The primary analysis is the validation of existing CDRs. The Wells DVT score will be computed in all participants with suspected DVT, and both the Wells' PE score and revised Geneva score will be computed in participants with suspected PE. Calibration will be assessed by comparing predicted and observed rates of confirmed VTE (Hosmer-Lemeshow 'goodness-of-fit test'), and discrimination will be assessed using the area under the receiver operating characteristics curve (c-statistic). Further, the proportion of participants with the combination of a non-high clinical probability and negative D-dimer test, and the false-negative rate of this combination (ie the proportion of participants with confirmed recurrent VTE among those with a non-high clinical probability and negative D-dimer) will be estimated along with their 95% confidence intervals.

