12.2 Central Independent Adjudication Committee (CIAC)

All cases of confirmed VTE will be adjudicated by independent adjudicators. The results of all imaging tests performed at the time of suspected recurrent VTE will be compared with the patient's previous imaging, baseline or index, when available, and will be performed according to the predefined definitions (Refer to **Appendix E**:

Adjudication of Suspected Recurrent VTE Events). The adjudicators will confirm or refute suspected recurrent DVT and PE events.

The adjudication committee will also evaluate secondary outcomes including all suspected VTE events and deaths occurring during the 90 (± 7) day follow-up period. The adjudication results will be the basis for the final analysis.

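### The rule-out combination tested in Section 9.5 is also an outcome criterion in Appendix E, so its false-negative rate is biased toward zero to the extent that this criterion overrides imaging or 90-day events go uncounted

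*Combined protocol and SAP*

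**What the plan says.** - **Appendix E**, opening paragraph: "Recurrent VTE will be excluded if participants have a low/intermediate or unlikely pre-test clinical probability with the Geneva or Wells rule", in combination with a negative D-dimer. No imaging or follow-up condition is attached.
- **Appendix E**, imaging criteria, equally unconditional. For CT, for example, if "an intraluminal filling defect is seen in a segmental or greater vessel that was previously free of thrombus, pulmonary embolism is diagnosed". No order is given between these criteria and the opening paragraph.
- **Section 9.5** defines the false-negative rate as "the proportion of participants with confirmed recurrent VTE among those with a non-high clinical probability and negative D-dimer". It gives no time window. Section 9.5.3 repeats the estimate for every stratification tool, also without a window.
- **Section 12.2** sends adjudicators to Appendix E and adds: "The results of all imaging tests performed at the time of suspected recurrent VTE will be compared with" previous imaging where available. It continues: "The adjudication committee will also evaluate secondary outcomes including all suspected VTE events and deaths" during the 90-day period, and then: "The adjudication results will be the basis for the final analysis".
- **Section 6.3**: "All patients in whom a recurrent VTE is ruled out will receive a follow-up call at 3 months".
- **Section 6.2.1** leaves the work-up to usual care, so some of this group will be imaged and some may not be.
- **Section 6.2.2**: "D-dimer levels will be determined in all patients using a single commercial assay", on frozen samples shipped in batches. Section 9.5 does not say whether this result or a local one defines the group.
- The **Protocol Summary** calls adjudication blinded but does not say to what.

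**The concern.** This is incorporation bias: the test being evaluated helps to decide who has the disease. A participant with a non-high category, a negative D-dimer and a new filling defect is excluded by one sentence of Appendix E and diagnosed by another. A participant who was not imaged and has a VTE on day 60 is excluded at presentation, and nothing says that the later event enters the Section 9.5 numerator.

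The false-negative rate is the safety part of the primary analysis, and a low value would support withholding imaging. Section 2.2 says that existing studies leave wide intervals on this question. Two analysts who follow the text could report different rates from the same data, and the readings that depart from full counting all err toward a lower rate.

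**Working it through.** **Inputs.** 345 participants with suspected DVT and 400 with suspected PE (Section 9.2). A yield of 10-16% for the combination (Section 2.2, D-dimer Testing). A 3-month failure rate of 0.75% (95% CI to 4.09%) after a negative D-dimer alone in suspected DVT (same section). The documents give no expected false-negative rate for the combination in this study, so 5% is used as an assumed upper scenario.

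**Plan's own figure.** 100/0.29 = 344.8, rounded up to 345; 100/0.25 = 400; total 745. This reproduces.

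**Group sizes.** DVT: 345 × 0.10 = 34.5 and 345 × 0.16 = 55.2, so about 35-55. PE: 400 × 0.10 = 40 and 400 × 0.16 = 64.

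**Effect per case and expected missed cases.** One case moves the rate by 1/n. The exact upper 95% limit for zero events is 1 − 0.025^(1/n). Expected missed cases are n × miss rate.

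| n | 1/n | Upper limit, 0 events | Expected at 0.75% | Expected at 5% |
|---|---|---|---|---|
| 35 | 2.9% | 10.0% | 0.26 | 1.75 |
| 55 | 1.8% | 6.5% | 0.41 | 2.75 |
| 40 | 2.5% | 8.8% | 0.30 | 2.00 |
| 64 | 1.6% | 5.6% | 0.48 | 3.20 |

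The upper limits reflect group size only; they show what would be reported if no case were counted.

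**How the reading changes the result.** As an illustration, take 64 PE participants and three true cases, one seen on imaging at presentation and two found by day 90. Both the number and the split are assumed.

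| Reading | Count | Rate (exact 95% CI) |
|---|---|---|
| Exclusion sentence outranks imaging; 90-day events not counted | 0/64 | 0% (0-5.6) |
| Imaging takes precedence; 90-day events not counted | 1/64 | 1.6% (0.04-8.4) |
| Exclusion sentence outranks imaging; 90-day events counted | 2/64 | 3.1% (0.4-10.8) |
| Imaging takes precedence and 90-day events counted | 3/64 | 4.7% (1.0-13.1) |

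**Text check.** Does any visible passage choose among these rows? Appendix E ranks nothing. Section 12.2 labels the 90-day events secondary outcomes. Sections 9.5 and 9.5.3 have no time window, whereas Section 9.5.5 does name a 3-month failure rate for its own question. Figure 1 and the Appendix C flow chart are not visible in the text reviewed and might show an order.

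**The case against.** The strongest reply is that this is an ambiguity and that the sensible reading is harmless. The imaging criteria are as unconditional as the exclusion sentence, and Section 12.2 has all imaging compared with earlier imaging, so the sentence probably covers only participants who were not imaged. Section 2.2 itself counts as a failure a patient whose DVT had been excluded by D-dimer and who had VTE within 3 months, so excluded does not mean beyond counting. The Section 12.2 statement on the final analysis directly follows the one on 90-day events. The D-dimer used for local exclusion may not be the central one. The size depends on an assumed miss rate, and Section 9.5 sets no acceptance limit that the rate could cross.

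Much of this stands. A reader might infer that the false-negative rate is zero by construction. The documents do not support that: it needs the exclusion sentence to outrank equally unconditional imaging criteria, and the same D-dimer result to be used in both places. Even then it is zero only at presentation, because 90-day events could still be counted.

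What does not stand is that the benign reading is in the plan. No visible passage says that imaging takes precedence or that 90-day events enter the Section 9.5 numerator. A flow chart of suggested care would not by itself define that numerator.

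**Conclusion.** The concern holds in this form: the strategy under test is part of its own reference standard, and its false-negative rate is biased toward zero to the extent that the exclusion sentence is applied over imaging or 90-day events are left out. If imaging takes precedence and 90-day events count, the remaining bias is smaller and lies mainly with participants who were not imaged and whose missed VTE does not surface in follow-up.

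Each miscoded case is worth 1.6-2.9 percentage points, given groups of 35-64. How many such cases there will be is unknown. At 0.75%, a figure for D-dimer alone in DVT, even the worst reading loses 0.3-0.5 expected cases per group. At an assumed 5% it loses 1.8-3.2. For the combination itself, Section 2.2 offers 0 of 16 in DVT, with an exact upper limit of 1 − 0.025^(1/16) = 20.6%, so the documents neither predict 5% nor rule it out.

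The same outcome also feeds calibration and the c-statistic. No effect on those was calculated and none is claimed. The wording should be settled before adjudication and analysis, because it affects a primary estimate and is cheap to correct.

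**What to change.** These changes concern outcome classification only and do not alter care.

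1. Remove the opening paragraph of Appendix E as an outcome criterion.
2. Use one outcome rule in Sections 9.5 and 9.5.3. VTE is present if adjudicated imaging at presentation, compared with baseline where available, is positive, or if adjudicated VTE or PE-related death occurs within the 90-day follow-up. The second limb applies after negative, indeterminate or no imaging.
3. State that the central D-dimer defines the rule-out group.
4. Mask rule category and D-dimer from adjudicators, and say so where adjudication is called blinded.
5. Report the rate also for participants imaged and not imaged at presentation, as a descriptive split because the groups are small.

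**Cost.** Wording in Appendix E, 9.5 and 9.5.3, and two items masked in the adjudication packets. Imaging comparison, the 90-day call and the central assay are already planned. Section 6.3 promises the call to participants in whom VTE is ruled out, so it should say whether those with indeterminate imaging are included.

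**Downsides.** The reported rate may rise above zero. Residual thrombus may be read as new where no baseline imaging exists, and a genuinely new event within 90 days may be counted as a miss; each such case adds 1.6-2.9 points. Follow-up may find only some of the missed cases among participants who were not imaged.

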Objectives	
Primary Objective: To assess the accuracy and usefulness of the Wells DVT, Wells PE and Geneva clinical decision rules in patients with a clinically suspected recurrent VTE.
 
Secondary Objectives:
 
• To assess the utility of recalibrating the existing clinical decision rules.• To derive a new CDR, specific to patients with a suspected recurrent VTE, and to assess whether this CDR would improve risk stratification as compared with existing CDRs.• To assess the accuracy of D-dimer testing in patients with suspected recurrent VTE both on and off anticoagulation.• To evaluate the accuracy of current CDRs in patients on anticoagulant therapy at the time of suspected recurrent VTE.
Duration	All consecutive eligible patients will be approached for enrolment into this study over 3 years.
Design	This is a multicentre, observational cohort study to prospectively identify potential predictors of recurrent VTE. The predictive value of individual and combined candidate predictors will be evaluated in patients with suspected recurrent VTE. All suspected recurrences will be blindly and independently adjudicated.
Significance	If the newly developed clinical decision rule is proven to accurately determine the pre-test probability in patients with a suspected acute recurrent VTE, it could be integrated in diagnostic strategies that might lower cost, avoid radiation exposure and potentially decrease over-diagnosis of patients with suspected recurrent VTE.

Target Sample Size A total of 745 participants will be enrolled at Canadian sites.

Participant Population

Inclusion Criteria

1. Outpatient with clinically suspected acute recurrent DVT or PE regardless of whether the previous event was a DVT or PE
2. Age ≥ 18 years old
3. Willing and able to give informed consent

Exclusion Criteria

1. Life expectancy less than 3 months
2. Suspicion of upper extremity thrombosis or thrombosis at an unusual site (e.g. cerebral or abdominal venous thrombosis)
3. Previous VTE was distal DVT or subsegmental PE
4. Suspected recurrent VTE is asymptomatic
5. Previously enrolled in this study

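### Adjudication is promised as blind, but the Appendix E outcome definition requires the Wells/Geneva class and D-dimer result that the primary analysis is meant to evaluate

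*Combined protocol and SAP*

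**What the plan says.** The Design row of the Protocol Summary states: "All suspected recurrences will be blindly and independently adjudicated". It does not say what the adjudicators are blind to.

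Section 12.2 refers the adjudicators to Appendix E for their definitions and adds: "The adjudication results will be the basis for the final analysis". The only material it names is imaging: "The results of all imaging tests performed at the time of suspected recurrent VTE will be compared with the patient's previous imaging, baseline or index," where that is available. It neither grants nor withholds access to the decision-rule (CDR) score or the D-dimer.

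Appendix E opens with a rule that is not about imaging. Recurrent VTE is excluded when "participants have a low/intermediate or unlikely pre-test clinical probability with the Geneva or Wells rule and a negative D-dimer test result". The DVT and PE criteria that follow rest on imaging alone.

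Section 9.5 states: "The primary analysis is the validation of existing CDRs". It plans calibration, the c-statistic, and the rate of confirmed VTE among participants with a non-high class and a negative D-dimer.

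**The concern.** In a diagnostic validation study the reference standard should be reached without the index tests. Here the index tests are the Wells and Geneva rules and the D-dimer, and the outcome definition contains them. Two things are at stake.

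The first follows directly from the text. A participant with a non-high class and a negative D-dimer has no recurrence by definition, and section 9.5 then estimates how often that same group has a recurrence.

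The second is a risk left open. Adjudicators who hold the class and D-dimer in order to apply the first rule may also have them in view when they judge an unclear image. Old and new thrombus are hard to tell apart in this population, so there is room for the class to tip the decision. Any such influence would favour the existing rules. It would also reach the coefficients of the new rule, because presenting symptoms and signs and the D-dimer are among its candidate predictors. No planned analysis would reveal it.

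**Working it through.** **Plan's own figures.** Section 9.2 needs 100 confirmed events of each type: 100/0.29 = 344.8, so 345 with suspected DVT; 100/0.25 = 400 with suspected PE; total 745. This reproduces and is not disputed. The implied prevalence is 200/745 = 26.8%, taken as 27% below.

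**Reading the sections together.**
1. Summary: adjudication is blind, with no object stated.
2. Section 12.2: adjudicators apply Appendix E, and their result is what is analysed.
3. Appendix E, first rule: its inputs are the CDR class and the D-dimer.
4. Section 9.5: the same class and the same class/D-dimer combination are evaluated.

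Steps 2 and 3 put the index tests in the adjudicators' hands. Step 1 therefore cannot hold for those tests. Appendix E also gives no precedence if a participant meets the first rule and has positive imaging. That can happen, because work-up is at the treating physician's discretion (6.2.1) and every participant has a central D-dimer (6.2.2).

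**Size of the group fixed by definition.** Section 2.2 puts the share excludable by low pre-test probability plus negative D-dimer at 10-16%. Of 745 that is about 75 to 119 participants. Their baseline false-negative count is zero by construction. The exact 95% upper limit for 0/n is 1 − 0.025^(1/n): 4.8% at n = 75 and 3.1% at n = 119. Those limits would be reported whatever the truth at baseline. Only follow-up events could alter the count, and 12.2 classes those as secondary outcomes.

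**Illustration for unclear images.** None of the following assumptions is in the documents, except that the prevalence is derived as above.
- Score: normal with unit variance, shifted by d = √2·Φ⁻¹(0.65) = 0.545 in true cases, so the true c is 0.65.
- Prevalence p = 0.27; share in the high class h = 0.40, which puts the cut-point at 0.406.
- Share of images unclear q; share of those called by class w; relabelled fraction m = q·w.

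Observed positives are (1−m)p true cases plus m·h high-class participants. Observed negatives are (1−m)(1−p) true non-cases plus m(1−h) low-class participants. The component c-statistics are 0.650 (cases against non-cases), 0.811 (cases against low class), 0.840 (high class against non-cases) and 1 (high against low class). The observed c is their average, weighted by the products of the group sizes.

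- q = 0.10, w = 0.10, m = 0.01: (0.2673×0.7227×0.650 + 0.2673×0.006×0.811 + 0.004×0.7227×0.840 + 0.004×0.006) / (0.2713×0.7287) = 0.1293/0.1977 = 0.654.
- q = 0.32, w = 0.50, m = 0.16: (0.2268×0.6132×0.650 + 0.2268×0.096×0.811 + 0.064×0.6132×0.840 + 0.064×0.096) / (0.2908×0.7092) = 0.1472/0.2062 = 0.714.

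| Unclear | w = 0 | w = 0.10 | w = 0.25 | w = 0.50 |
|---|---|---|---|---|
| 10% | 0.650 | 0.654 | 0.660 | 0.670 |
| 20% | 0.650 | 0.658 | 0.670 | 0.690 |
| 32% | 0.650 | 0.663 | 0.682 | 0.714 |

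For scale, the Hanley-McNeil standard error of a c-statistic of 0.65 with 100 events and 245-300 non-events is about 0.033. The inflation therefore runs from 0.004/0.033 = 0.1 to 0.064/0.033 = 1.9 standard errors.

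**The case against.** A reader might infer that equivocal images are in fact judged with knowledge of the class, in every risk category. The documents do not support that. Every DVT and PE criterion in Appendix E refers only to imaging, and 12.2 describes a comparison of images. The class/D-dimer rule is needed only for participants whom it excludes; using it there does not require showing the class when another participant's scan is read. The word blindly might also refer to something else, such as the local diagnosis. All of this stands, so the effect on unclear images is a possibility and not a stated procedure.

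The background imaging figures in section 2.1 do not give an unclear-image rate for this cohort either. The 20% were positive scans that baseline imaging resolved as unchanged, and Appendix E rules such findings out for DVT and for PE on CT or V/Q. The 32% concerns ultrasound in suspected ipsilateral recurrent DVT only, whereas 400 of the 745 planned participants have suspected PE. The rate at which adjudicators would follow the class is pure assumption.

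The objection does not remove the conflict between the blinding promise and the first rule of Appendix E. Nor does it close the gap. The plan withholds nothing, the adjudication report for follow-up events draws on medical records with no mention of redaction (6.3), and Appendix E has no rule for indeterminate imaging although 9.5.5 expects it.

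**Conclusion.** The contradiction is certain and rests on the text alone: the adjudicators' definition uses the tests whose accuracy is the primary objective. It follows that the reference standard is not independent of those tests for roughly 75-119 participants, if the 10-16% in section 2.2 carries over to this cohort.

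Bias in the c-statistic through unclear images is conditional and of unknown size. Under the stated assumptions a true 0.65 would be observed as about 0.654 to 0.714, and with no influence of the class it stays at 0.65 as far as this mechanism goes. That range shows what is at risk; it is not an estimate of what will happen. The point should be settled before adjudication starts, since unblinded adjudication can be repaired only by repeating it.

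**What to change.** 1. **Section 12.2.** State that adjudicators are blinded to CDR scores and class, D-dimer results, the physician's estimated likelihood, and presenting symptoms and signs. They keep current and previous imaging, the location and side of the previous event, and follow-up information. Do not remove every Appendix D item, because that list includes previous-event and baseline-imaging data needed for the comparison.
2. **Appendix E.** Remove the class/D-dimer sentence from the adjudicators' criteria. Identify participants who had no imaging because of CDR plus D-dimer as a separate category outside adjudication. Take their outcome from the 3-month follow-up that 6.3 already collects, and do not set it to no VTE by the rule. Say in 9.5 that these follow-up events count.
3. **Indeterminate imaging.** Add it as an adjudication category, report it as such, and run a sensitivity analysis coding these cases first all positive and then all negative.
4. **Scope.** Align the opening of 12.2, "All cases of confirmed VTE will be adjudicated by independent adjudicators", with the Summary, which covers all suspected recurrences.

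The cost is redaction work on the adjudication packs, short edits to 12.2, 9.5 and Appendix E, and a few more cases called indeterminate. Sample size, visits and patient care do not change.

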Post-hoc analyses of diagnostic studies have been reassuring in terms of the safety of ruling out VTE on the basis of a non-high pretest probability using the Wells or Geneva rule in combination with a negative D-dimer in patients with a previous history of VTE.^{4,9} However, the proportion of patients in whom the diagnosis could be ruled out non-invasively was very low: approximately 10%, as compared with 30% among all-comers with suspected VTE.¹⁰

Moreover, residual thrombosis is often present after a VTE event (up to 50% of patients at one year). Therefore, it is more likely to misdiagnose a recurrent VTE in saying it is present, while it's absent. As a result of over diagnosis, these patients have a long period of exposure to anticoagulants and the associated risk of major bleeding.

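### Appendix E requires a new finding for ultrasound, V/Q and CT but not for venography or pulmonary angiography, so residual thrombus on those two tests can be counted as recurrence

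*Combined protocol and SAP*

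**What the plan says.** Appendix E of the combined protocol and SAP defines a positive result for five imaging tests. Three of the definitions depend on change from earlier imaging:

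- Ultrasound (DVT criterion 1): "Compression ultrasound revealing a new (compared to baseline/index ultrasound) area of non compressibility of a venous segment".
- V/Q (PE criterion 2): "a new unmatched segmental or greater perfusion defect is documented then recurrent PE will be diagnosed".
- CT (PE criterion 4): "intraluminal filling defect is seen in a segmental or greater vessel that was previously free of thrombus".

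Each of these three also has a sentence that excludes recurrence when the result is unchanged.

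The other two definitions have no such condition:

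- Venography (DVT criterion 2): "Venography demonstrating a constant intraluminal filling defect in the deep veins above the trifurcation of the popliteal vein will be considered diagnostic".
- Pulmonary angiography (criterion 5 for PE): "Pulmonary angiography demonstrating a constant intraluminal filling defect or a cutoff of a vessel > 2.5 mm in diameter will be considered diagnostic for PE".

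The two DVT criteria are joined by OR.

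Section 12.2 says that imaging from the suspected event is compared with baseline or index imaging when that exists, that adjudication follows the Appendix E definitions, and that the final analysis rests on the adjudicated results. Section 6.2.3 describes compression ultrasound for suspected DVT, and CTPA or V/Q for suspected PE. It does not mention venography or pulmonary angiography.

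**The concern.** The study exists largely because old clot is hard to tell from new clot. Section 2.1 says that "residual thrombosis is often present after a VTE event (up to 50% of patients at one year") and describes over-diagnosis, with its bleeding risk, as a main harm. It also cites a study in which 20% of patients with a suspected recurrence had imaging that was positive but unchanged from baseline. A definition that lets a persisting defect count as recurrence works against that rationale.

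The adjudicated diagnosis is the reference standard for everything in section 9: calibration and c-statistics of the existing rules, the recalibrated and modified rules, and the new rule. A false positive in the reference standard counts as a confirmed event in each of these. If the definition depends on which test happened to be done, or if two adjudicators can read it differently, the outcome does not have one meaning across participants.

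**Working it through.** **Step 1. The criteria side by side (Appendix E).**

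| Test | Finding must be new? | Unchanged finding excluded? |
|---|---|---|
| Compression ultrasound, DVT criterion 1 | Yes | Yes, also if improved, when a baseline is available |
| Venography, DVT criterion 2 | Not stated | Not stated |
| V/Q scan, PE criteria 1 and 2 | Yes | Yes |
| CT, PE criterion 4 | Yes | Yes |
| Pulmonary angiography, PE criterion 5 | Not stated | Not stated |

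**Step 2. Can the rules conflict for one participant?** Take a participant whose ultrasound shows an incompressible segment unchanged from baseline, and whose venogram shows a constant defect at the same site. The ultrasound sentence rules recurrence out, while criterion 2 is met and confirms it. The PE criteria allow the same conflict: an unchanged CT excludes PE under criterion 4, and a persisting angiographic defect is diagnostic under criterion 5. Appendix E gives no order of precedence. This is a possible sequence of tests; the protocol does not describe it as an expected one.

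**Step 3. Does section 12.2 close the gap?** Only in part. It requires the comparison, and its scope covers these two tests. It then refers the adjudicators to the Appendix E definitions. For venography and angiography those definitions do not say how the comparison changes the result. An adjudicator could compare, see no change, and still find the written criterion met.

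**Step 4. Size.** No figure in the plan depends on this point. For reference, the planned sample reproduces: 100 / 0.29 = 344.8, rounded up to 345 with suspected DVT; 100 / 0.25 = 400 with suspected PE; 345 + 400 = 745 (section 9.2).

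The share of participants decided on venography or angiography is not given. As an illustration only, let *f* be that share and *r* the fraction of those participants who show residual thrombus alone. Both *f* and *r* are assumptions. The values of *r* are borrowed from section 2.1 (20% positive but unchanged; up to 50% residual thrombosis at one year), and neither is reported there for these two tests. If no comparison is made at all:

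misclassified positives x = 745 × *f* × *r*; share of confirmed events = x / (200 + x), where 200 is the planned 100 DVT plus 100 PE.

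| *f* | *r* | x | x / (200 + x) |
|---|---|---|---|
| 0% | any | 0 | 0% |
| 1% | 20% | 1.49 | 1.49 / 201.49 = 0.7% |
| 1% | 50% | 3.73 | 3.73 / 203.73 = 1.8% |
| 5% | 20% | 7.45 | 7.45 / 207.45 = 3.6% |
| 5% | 50% | 18.6 | 18.6 / 218.6 = 8.5% |

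The table shows only that the effect scales with a share that the plan does not give, and that zero is within its range.

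**The case against.** The strongest answer is section 12.2. Its comparison with previous imaging is not limited to certain tests, and independent adjudicators decide each event. A sensible adjudicator who sees an unchanged venogram would probably not call it a recurrence. This stands in part: it makes misclassification less likely but leaves the written criteria inconsistent. A reader might infer from Appendix E alone that residual thrombus on these tests *will* be adjudicated as recurrence, or that the definitions make the comparison irrelevant. The documents support neither reading. They support *can be, if the two criteria are applied literally*.

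The second answer is that these tests may never be used. Section 6.2.3 names only compression ultrasound, CTPA and V/Q. This also stands, and it limits the size of the point. It does not remove the point, because work-up follows local practice at the physician's discretion (sections 3 and 6.2.1) and the authors did write criteria for both tests. The Appendix C flow chart was not available in the text reviewed, so whether it names either test was not checked. The documents also do not say that these tests are reserved for unclear first-line imaging, so no argument should rest on that.

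Third, a reader might infer that misclassified cases inflate the false-negative rate of a non-high probability with a negative D-dimer. The documents do not support a figure. Nothing places such cases in that group. Section 2.1 says imaging is needed for patients at high risk or with a positive D-dimer, so this group is the least likely to reach these tests. The first rule of Appendix E also excludes recurrence in participants with a non-high probability and a negative D-dimer.

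**Conclusion.** The inconsistency is real and can be seen within Appendix E. Two of the five imaging definitions lack both the requirement for a new finding and the exclusion for an unchanged one, and section 12.2 does not fully supply what is missing. Read literally, the rules can confirm residual thrombus as recurrence and can give opposite answers for one participant.

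The point is minor. The number affected is unknown and may be zero. The figures above rest on an assumed rate of use, on fractions borrowed from other settings, and on no comparison being made, so they are not estimates for this study. The sample size of 745 is unaffected. What can be said firmly is that the reference standard is not defined in the same way for every test.

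**What to change.** Reconcile Appendix E with section 12.2 in two places. In DVT criterion 2 and PE criterion 5, state that the defect, or for angiography the defect or cutoff, must be new compared with baseline or index imaging when available. Add that an unchanged finding on either test is not counted as recurrence. The word *new* is enough. Requiring that the site was previously shown to be free of thrombus would be stricter than the ultrasound and V/Q criteria, and could leave a true recurrence unconfirmed at a site never imaged before.

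Where no earlier imaging exists, Appendix E has no explicit rule for any test. Whatever convention the adjudicators adopt should be written down and applied equally to all five.

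The cost is a few lines of text, with no new data, visits or participants. The downside is that a few events may no longer count as confirmed.
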